4.0 Objectives

4.1 Primary Objectives

1. Quantify number of CR, PR, MR, SD and progressions in response to dosimetry-guided PRRT utilizing RECIST 1.1 criteria and ⁶⁸Ga-DOTATOC or ⁶⁸Ga-DOTATATE PET to evaluate efficacy of ⁹⁰Y-DOTATOC therapy in children and adults with neuroendocrine and other somatostatin receptor positive tumors.
2. Monitor renal, hematologic, and clinical toxicities associated with dosimetry-guided ⁹⁰Y-DOTATOC PRRT while maximizing total tumor dose and limiting total renal dose of ⁹⁰Y-DOTATOC to ≤ 23 Gy.

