9.1 Adverse Events List and Reporting Requirements

As with any new drug, this study may involve risks that are currently unforeseeable. The most frequent adverse events observed in adults treated with these drugs are listed below.

Severity of adverse events will be graded according to NCI Common Terminology Criteria for Adverse Events version 4.0 (CTCAE v4.0) which is available at <http://ctep.cancer.gov/reporting/ctc.html>.

Adverse events will be collected from time of consent until 30 days post ⁹⁰Y treatment. Labs will only be collected as adverse events if deemed clinically significant by the investigator. Serious Adverse Events (SAE's) that occur >30 days after the last ⁹⁰Y treatment will only be reported if at least possibly related to investigational product.

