9.1.1 Routine Adverse Event Reporting Requirements to DSMC

An adverse event (AE) is defined in the *CTEP, NCI Guidelines* [2005] as "any unfavorable and unintended sign (including an abnormal laboratory finding), symptom or disease temporally associated with the use of a medical treatment or procedure (attribution of unrelated, unlikely, possible, probably or definite)."

Routine adverse events will be reported by submission of an adverse events log to the DSMC at the time of DSMC review.

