Treatment efficacy, defined as a complete response, partial response or stable disease (CR+PR+SD), is the primary endpoint of interest in this dosimetry-guided Phase II trial. Tumor response will be defined according to RECIST1.1 criteria applied on up to five target lesions (primary tumor if not surgically removed, up to two liver lesions, up to two nodal metastases, metastatic lesion in other organs, such as ovary, breast) that will be quantified and compared between pre-therapy and 3-9 months post-therapy high-resolution, contrast-enhanced CTs. Osseous metastases may be followed as non-target lesions. ⁹⁰Y-DOTATOC will be deemed worthy of further study if its associated response rate is ≥ 0.60 , and clinically uninteresting if its rate is ≤ 0.40 . Enrollment will proceed according to an optimal Simon two-stage study design. Sixteen (16) subjects will be enrolled in the first stage; if 7 or fewer patients respond, the arm will be closed and the treatment ruled clinically uninteresting. Otherwise, an additional 30 subjects will be enrolled. If 24 or more responses are observed in the total of 46 subjects, then the treatment will be ruled worthy of further study. The study design has a probability of early termination equal to 0.72. Power to detect efficacy is 0.80 with a type 1 error rate of

0.05.

Secondary analysis will focus on time to tumor progression and overall survival. The method of Kaplan- Meier will be used to estimate progression and survival rates. Subjects for whom the outcome of interest is not observed at the 6 month follow-up will be treated as censored observations in the survival analysis.

12.2 Primary Objective 2

Adverse events will be recorded and reported in tabular form by type and grade. If four or more subjects experience renal toxicity \geq Grade 4, the radiopharmaceutical will be declared too toxic and the trial will be stopped. If any other irreversible Grade 4 toxicity is observed in four or more subjects, the treatment will be declared too toxic and will be stopped. Adverse events will be graded according to the most recent CTE guidelines.

12.3 Secondary Objective 1

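### Section 9.1 admits laboratory abnormalities as adverse events only on the investigator's judgment, so the laboratory rows of the section 12.2 toxicity table, mainly lower and intermediate grades, can be under-counted

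*Combined protocol and SAP*

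**What the plan says.** - **Section 4.1, primary objective 2:** "Monitor renal, hematologic, and clinical toxicities associated with dosimetry-guided" treatment, within the renal dose limit.
- **Section 12.2, analysis of that objective:** "Adverse events will be recorded and reported in tabular form by type and grade". The section then sets two stops, each at four or more subjects. For renal toxicity of Grade 4 or worse, "the radiopharmaceutical will be declared too toxic and the trial will be stopped". The second begins "If any other irreversible Grade 4 toxicity is observed in four or more subjects".
- **Section 9.1, the collection rule:** "Labs will only be collected as adverse events if deemed clinically significant by the investigator". Clinical significance is not defined, and no grade or organ system is exempt. Adverse events are collected from consent until 30 days after treatment.
- **Section 9.1.1, the definition:** an adverse event is "any unfavorable and unintended sign (including an abnormal laboratory finding), symptom or disease temporally associated with the use of a medical treatment or procedure". Routine events reach the DSMC as an adverse event log.
- **Section 7.0, the calendar:** blood counts with differential, creatinine, AST and ALT are scheduled at baseline, on Day 1 of the cycles and at both follow-up visits. Nuclear GFR is measured in children, and in adults whose creatinine exceeds the stated limit.
- **Appendix II, the monitoring plan:** accumulated AE and SAE reports are compared with the stopping rules.

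**The concern.** Two of the three kinds of toxicity named in primary objective 2 are detected mainly in the laboratory. Under section 9.1 an abnormal value counts only after the investigator has judged it significant. There is no control group, and neither blinding nor independent adjudication of toxicity is described. Two staff members following sections 9.1 and 9.1.1 could log different events from the same blood count.

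The filter can remove laboratory events but cannot add any, so an error from it lowers the reported rates. At stake is the laboratory part of the result for a primary objective. The lower and intermediate grades are the most affected, because there a judgment of not significant is easiest to reach.

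**Working it through.** The plan states no operating characteristics for toxicity, so there is no figure to reproduce. The check is to trace how a laboratory value reaches the result, and then to illustrate the effect under stated assumptions.

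**Path of a laboratory value**

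1. The value is measured on schedule (section 7.0), so the raw data exist.
2. It becomes an adverse event only if judged clinically significant (section 9.1).
3. Only adverse events enter the table (section 12.2).
4. No other section sends scheduled values to that table. Section 10.1 has numeric GFR and creatinine triggers, but they govern individual dosing and DLT status.

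A value that is abnormal by CTCAE but judged not significant is therefore missing from the table although the plan has been followed.

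**Illustration for the table (assumptions only)**

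Let c be the share of true laboratory toxicities that pass the filter. The expected tabulated rate is the true rate × c. Take a true count of 6 in 46, where 46 is the total in section 12.1 and 6 is assumed:

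- full capture: 6/46 = 13.0%
- c = 0.75: 13.0% × 0.75 = 9.8%
- c = 0.50: 13.0% × 0.50 = 6.5%

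The proportional loss is 1 − c whatever the sample size, so it does not depend on whether the total is 46 (section 12.1) or 64 (section 8.2).

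**Illustration for one stop (assumptions only)**

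If the count came solely from filtered reports, the chance of reaching four would be P(X ≥ 4), with X binomial(N, true rate × c). With an assumed true rate of 10%:

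| N | c = 1 | c = 0.9 |
|---|---|---|
| 46 | 0.688 | 0.604 |
| 64 | 0.894 | 0.839 |

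For Grade 4 values c is probably close to 1, and the difference vanishes as c approaches 1. Nothing in the documents supports a much lower c at that grade.

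**The case against.** The strongest case on the other side has five parts.

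- **The stops are worded on fact.** Section 12.2 refers to toxicity that subjects experience or that is observed, not to logged events. This stands. A reader might infer that the filter would delay or prevent a stop, but the documents do not support that. The only link is the monitoring item in Appendix II, and Grade 4 values are unlikely to be called insignificant.
- **The DSMC is not confined to the log.** Appendix II provides for review of study data at least twice a year, source comparison for at least 25% of subjects, and continuous access to subject data summaries. This also stands, so one cannot say that filtered values never reach the DSMC. However, an omission that complies with section 9.1 would not show up as an error on source checking, and none of these steps grades the values for the table.
- **Section 10.1 sets numeric renal triggers.** A GFR fall that compels a protocol action is hard to dismiss, so large GFR falls are the least likely losses. Blood counts have no such trigger in section 10.1.
- **Sections 9.1 and 9.1.1 need not conflict.** A reader might infer a flat contradiction. Yet the word unfavorable in section 9.1.1 already calls for judgment, and a definition followed by a collection threshold is a common arrangement. What stands is that the two sections set different bars and the plan does not say which one governs the table.
- **A significance filter is normal practice.** That is fair for incidental tests. Here the filtered tests are the main measures for a primary objective, and section 9.2 itself names anemia, low white cells, low platelets and permanent loss of kidney function as known effects.

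**Conclusion.** The concern holds for the section 12.2 table. As written, an undefined investigator judgment can remove laboratory toxicities from the result for a primary objective, and any bias from it is toward under-reporting. The effect should fall mainly on lower and intermediate grades. The stops are exposed in form only, through the Appendix II comparison, and this is a secondary point.

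No size can be derived from the documents. The fall from 13.0% to 9.8% or 6.5% rests entirely on an assumed true count and assumed capture shares, and the stop probabilities rest on an assumed 10% rate. They show the mechanism and do not estimate it. Because the raw values are collected anyway, the defect can be repaired without new data.

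**What to change.** Amend sections 9.1 and 12.2 as follows.

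1. Assign CTCAE v4.0 grades by program to every protocol-scheduled blood count with differential, creatinine and, where done, nuclear GFR, whether or not the value was judged clinically significant.
2. In section 12.2, tabulate each subject's worst post-baseline grade against the baseline grade (a shift table). Entry allows neutrophils down to 1000/mm³ and platelets down to 90,000/mm³, so without the baseline grade a pre-existing abnormality would be shown as toxicity.
3. State that this table includes the scheduled follow-up values even when they fall outside the 30-day adverse event window.
4. Give the DSMC the list of laboratory-graded Grade 4 values when it checks the section 12.2 stops. Leave the stopping criteria as they are, including the condition that non-renal toxicity be irreversible.
5. Keep the clinical-significance filter for other laboratory tests, and reconcile section 9.1 with section 9.1.1.

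The shift table should stand beside the adverse event table and not replace it, because abnormalities found between scheduled visits will still come only through the log.

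The cost is a few sentences of protocol text and a small programming step on values already collected, with no new tests or visits. The reported rate of laboratory toxicity may be higher.

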9.1.1 Routine Adverse Event Reporting Requirements to DSMC

An adverse event (AE) is defined in the *CTEP, NCI Guidelines* [2005] as "any unfavorable and unintended sign (including an abnormal laboratory finding), symptom or disease temporally associated with the use of a medical treatment or procedure (attribution of unrelated, unlikely, possible, probably or definite)."

Routine adverse events will be reported by submission of an adverse events log to the DSMC at the time of DSMC review.

9.1.2 Expedited Adverse Event Reporting to DSMC

Serious adverse events occurring during study procedures with ^{90}Y -DOTATOC will require a notification to the DSMC as described in the Data and Safety Monitoring Plan (see appendix 1) below regardless of attribution to study intervention. The investigator will continue to follow or obtain documentation until the resolution of such an event until it is resolved (with or without sequelae)

9.1.3 Adverse Event Reporting Guidelines –

Documentation will begin after radiotracer injection and continue through 1 calendar day following imaging. This study will use the guidelines developed by the Cancer Therapy Evaluation Program (CTEP) for PET and/or SPECT IND agents. For purposes of the below table, it should be noted that the radioactive half-life for ^{90}Y is 64.1 hours. Therefore, 10 radioactive half-lives will be 27 days for the purposes of adverse event reporting.

9.2 Expected Adverse Events Associated with ^{90}Y -DOTA-tyr³-Octreotide (^{90}Y -DOTATOC)

Treatment involves administering a radioactive drug into the bloodstream from where it may attach to any cell (cancerous and healthy) that has somatostatin receptors on its surface and normally comes in contact with somatostatin. Therefore, healthy cells may potentially be killed or damaged by this drug. Healthy cells that contain somatostatin receptors are present in the pancreas, stomach, duodenum, small intestine, large intestine, pituitary, and ovaries. No damage to these organs has been seen in the adults who have taken this drug. Other healthy organs which do not contain somatostatin receptors but which normally come in contact with somatostatin include the bladder.

Kidney exposure is due to the renal clearance of this drug as well as the normal amino acid recirculation mechanism that operates to conserve amino acids and small peptides. The kidney contains somatostatin receptors and also comes in contact with ^{90}Y -DOTATOC as it is being excreted. This means the kidney usually receives the most radiation of any normal tissue in the body. Adult humans who have received ^{90}Y -DOTATOC have experienced some damage to the kidney. Some adults have experienced permanent decrease in kidney function, but no adults have required dialysis. **There is a risk that severe kidney damage could occur which may result in the need for permanent dialysis. Kidney damage may occur as a late effect, months after the last dose of ^{90}Y -DOTATOC.**

Adults and children have been treated with ^{90}Y -DOTATOC. Side effects that were observed include: bowel obstruction, diarrhea, weight loss, reduced red blood cells (anemia), reduced white blood cells (increased chance of infection), and reduced platelets (increased chance of uncontrolled bleeding). These effects depended on the dose of ^{90}Y -DOTATOC and occurred at higher doses tested. Most patients recovered from these effects after stopping ^{90}Y -DOTATOC; however, two patients (of a total of over 2500 patients treated as of 12/31/13) have developed myelodysplastic syndrome.

An unexpected allergic reaction following the administration of ^{90}Y -DOTATOC or the amino acids may consist of shortness of breath, wheezing, lowering of blood pressure, fever, chills, hives, itchiness or damage to the blood vessels. The amino acid solution is hyperosmolar and may cause local inflammation or in rare cases, blistering at the infusion site. A 20 gauge IV line or PICC line is recommended to avoid this inflammation. A phone call will be made to subjects 3-5 days following each infusion of amino acids to assess skin changes at the injection site. The long-term effects of ^{90}Y -DOTATOC are unknown. ^{90}Y -DOTATOC may cause radiation damage that may not surface until months or years later.

Participation in this study may be hazardous to a fetus or a nursing child. There is not enough information to determine whether there are significant risks to a nursing child or a fetus conceived or

carried by a subject who is participating in this study. Therefore, in order to participate, all females capable of becoming pregnant must have a negative pregnancy test within 7 days prior to the first ^{90}Y -DOTA-tyr³-octreotide treatment. Female subjects must tell us if they may have become pregnant within the previous 14 days because the pregnancy test is unreliable during that time. All subjects capable of becoming pregnant must agree to practice a medically acceptable birth control measure (abstinence, birth control pills, intrauterine devices, vaginal diaphragm, vaginal sponge, or condom with spermicidal jelly) throughout the study and for eight months following the end of the last treatment. Any females who are nursing must refrain from nursing while on study and for three months following the end of the last treatment.

9.3 Expected Adverse Events Associated with Amino Acid Infusions:

Generalized flushing, fever, and nausea have been reported during infusions of amino acid solutions. Local reactions consisting of a warm sensation, redness, inflammation of the vein and blood clotting at the infusion site have also occurred. Low or high potassium and phosphate levels have been observed in some adult patients. These levels have not been clinically significant and have returned to within normal limits after completion of therapy except in one case out of more than 400 individual infusions of amino acids. To avoid this rare electrolyte disturbance, we will check heart rate and potassium level 60 min prior to end of amino acid infusion; if >6 meq/L and/or heart rate < 60 bpm, we will administer oral or IV NaHCO_3 and keep patient sitting or supine until heart rate >65 bpm.

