11. The effects of ⁹⁰Y-DOTA-tyr³-Octreotide on the developing human fetus are unknown. For this reason and because Class C agents are known to be teratogenic, women and men of child-bearing potential must agree to use adequate contraception (hormonal or barrier method of birth control) prior to study entry and for the duration of study participation. Should a woman become pregnant or suspect she is pregnant while participating in this study, she should inform her treating physician immediately.
12. Ability to understand and the willingness to sign a written informed consent document.

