6.0 Imaging and Treatment Plan

**Phase II,
Dosimetry-Guided, Peptide Receptor Radiotherapy (PRRT) with
⁹⁰Y-DOTA-tyr³-Octreotide (⁹⁰Y-DOTATOC) in Children and Adults
with Neuroendocrine and other Somatostatin Receptor Expressing Tumors**

Treatment Cycles and Followup		Imaging and Treatment Schedule	Initial ⁹⁰ Y-DOTATOC Dose	Cumulative ⁹⁰ Y-DOTATOC Dose	Cumulative Renal Radiation
Cycle 1 Week 1	Day 1	Physical exam with height, weight, vitals, labs, list, GFR, pregnancy test; QOL questionnaire Start 18 hrs IV/PO fluids			
	Day 2	⁹⁰ Y-DOTATOC + IV amino acids Continue IV/PO fluids for 48 hrs	50 mCi/m ² in children; 120 mCi in adults	120 mCi maximum	
	Day 4	⁹⁰ Y-DOTATOC PET/CT			
Cycle 2 Week 7-9	Day 1	Physical exam with height, weight, vitals, labs, med list, GFR, pregnancy test Start 18 hrs IV/PO fluids			
	Day 2	⁹⁰ Y-DOTATOC + IV amino acids Continue IV/PO fluids for 48 hrs	Dosimetry determined	270 mCi maximum	
	Day 4	⁹⁰ Y-DOTATOC PET/CT			
Cycle 3 Week 13-17	Day 1	Physical exam with height, weight, vitals, labs, list, GFR, pregnancy test Start 18 hrs IV/PO fluids			
	Days 2-3	⁹⁰ Y-DOTATOC + IV amino acids Continue IV/PO fluids for 48 hrs	Dosimetry determined	420 mCi maximum	≤ 23 Gy
FU	3 months after treatment 3	Physical exam with height, weight, vitals, labs, med list, GFR; QOL questionnaire, diagnostic CT (MRI)			
	6-9 months after treatment 3	Physical exam with height, weight, vitals, labs, med list, GFR; diagnostic CT (MRI) ⁶⁸ Ga-DOTATOC PET/CT;			

Treatment consists of 3 cycles, 6-8 weeks apart. Cycle 1 dose is fixed. Cycles 2 and 3 doses will be determined by dosimetry-based calculation of renal doses from previous cycles; total renal dose ≤ 23Gy.

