8.0 Duration of Therapy and Stopping Rules

8.1 Stopping Rules for individual subject

In the absence of treatment delays due to adverse events, treatment may continue for 3 cycles or until one of the following criteria applies:

- Cumulative renal radiation dose exceeds 23 Gy.
- Intercurrent illness prevents further administration of treatment.
- Unacceptable adverse event(s) such as irreversible renal or hematopoietic toxicity.
- Initiation of another tumor specific therapy.
- Patient decides to withdraw from the study.
- General or specific changes in the patient's condition render the patient unacceptable for further treatment in the judgment of the investigator.

Other causes of discontinuation from study:

- Termination of study by Sponsor.
- Subject's condition no longer requires study drug.

* Note: Disease progression alone does not mandate discontinuation of ⁹⁰Y treatment.*

Disease progression per RECIST 1.1 criteria during the follow up period will warrant removal from study.

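### Inclusion criterion 11 and the eligibility form give a different contraception period, population and method list from Section 9.2, and nothing reconciles them

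*Combined protocol and SAP*

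**What the plan says.** Two rules on contraception stand in the current text.

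- **Section 5.1, criterion 11.** It states that "women and men of child-bearing potential must agree to use adequate contraception". The methods are hormonal or barrier, and the period is "prior to study entry and for the duration of study participation". Nothing is required after participation ends. Item 11 of the inclusion form in Appendix III repeats this rule.
- **Section 9.2.** It states that "All subjects capable of becoming pregnant must agree to practice a medically acceptable birth control measure". The period is "throughout the study and for eight months following the end of the last treatment". The methods listed are abstinence, birth control pills, intrauterine devices, diaphragm, sponge, and condom with spermicide.

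The following provisions decide when participation ends:

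- **Section 8.1** lists "Patient decides to withdraw from the study" among the individual stopping criteria. It adds: "Disease progression per RECIST 1.1 criteria during the follow up period will warrant removal from study".
- **Section 6.0** places the last scheduled visit at "6-9 months after treatment 3". The Section 7.0 calendar has a 3-4 month visit and a 6-9 month visit, each with a diagnostic CT or MRI.
- **Section 7.0, note 8,** keeps subjects who stop dosing early on the follow-up schedule if they have had at least one dose.
- **Section 10.3** requires every subject with at least one dose to enter a Long-Term Follow-up Study Period once treatment stops. It gives no length for that period.

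**The concern.** This is a fetal-safety rule for a therapeutic radiopharmaceutical, and Section 9.2 itself warns of possible hazard to a fetus. A reader of criterion 11 and a reader of Section 9.2 would give a subject different end dates whenever participation ends less than eight months after the last treatment.

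The version without the eight months is also the one on the form that the investigator signs. Under Appendix II the completed eligibility checklist is uploaded for ongoing review by data and safety monitoring staff, and eligibility is among the items monitored. The eight-month requirement appears only in an adverse-event narrative, and criterion 11 does not refer to it. The Section 7.0 calendar schedules no pregnancy test at either follow-up visit, so the visit schedule would not expose a discrepancy.

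**Working it through.** There is no figure in the plan to reproduce. The check is a comparison of the texts followed by subtraction on the visit schedule.

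**Comparison**

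| Feature | Section 5.1, criterion 11, and Appendix III form | Section 9.2 |
|---|---|---|
| Who | Women and men | Only subjects who can become pregnant |
| Ends | With study participation | Eight months after last treatment, and not before the study ends |
| Anchor event | End of participation | Last treatment |
| Methods | Hormonal or barrier | A list that fits hormonal or barrier for the most part, plus abstinence and intrauterine devices |

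**Gap in end dates, for subjects who can become pregnant**

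Let t be the months from last treatment to the end of participation. Criterion 11 ends at t. Section 9.2 ends at the later of t and 8, because it also runs throughout the study. The gap is therefore

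G = max(0, 8 − t).

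Inputs: 8 months from Section 9.2; the exit routes from Section 8.1; visit times of 3-4 and 6-9 months from Sections 6.0 and 7.0.

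| How participation ends | t (months) | G (months) |
|---|---|---|
| Withdrawal right after the last dose | 0 | 8 − 0 = 8 |
| Removal for progression at the 3-4 month visit | 3 to 4 | 8 − 3 = 5, to 8 − 4 = 4 |
| Completion at the early edge of the final visit | 6 | 8 − 6 = 2 |
| Completion at 8 to 9 months | 8 to 9 | 0 |

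The final-visit window thus gives 0 to 2 months. Subjects who finish on schedule from month 6 to just before month 8 are affected as well as those who leave early.

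**What the arithmetic assumes**

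Each row takes participation to end at the named event. If the Long-Term Follow-up Study Period counts as participation, t is larger and G is smaller, possibly zero, for completers and for subjects who only stop dosing. Its length is not stated, so the reduction cannot be computed.

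**Men**

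The formula does not apply to men. Section 9.2 does not cover them, and criterion 11 covers them only until participation ends.

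**A parallel mismatch**

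The two parts of the protocol also differ on breastfeeding: Section 5.2 gives six weeks after the last administration and Section 9.2 gives three months after the last treatment. This suggests text that was not synchronized rather than two deliberately layered rules.

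**The case against.** The strongest reply is that the rules are cumulative. Both are worded as things subjects must agree to. A subject who can become pregnant meets both durations by following Section 9.2, which contains the criterion 11 period. This stands in part. A reader might infer that criterion 11 is the binding rule and that it releases subjects months early. The documents do not support that: nothing ranks Section 5.1 above Section 9.2, and early release would follow only if a site overlooked Section 9.2. What remains is that the criterion and the signed form omit a requirement stated elsewhere, and that the populations and methods differ too.

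A reader might also infer that anyone who leaves early is covered by one rule and not the other. That fails for men, whom neither rule covers after participation.

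A third inference would be fixed gaps of 2, 5 and 8 months. The visit windows make the first two into ranges, 8 months is the extreme case, and all depend on when participation ends. Stopping treatment is not leaving the study, as Section 7.0, note 8, and Section 10.3 make clear. This objection stands as a limit on the size. It does not remove the conflict, since withdrawal and removal for progression are explicit exits and the calendar shows no visit after 6-9 months.

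The methods difference is small: most of the Section 9.2 list fits hormonal or barrier. The clear addition is abstinence; intrauterine devices may be one, depending on type.

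Finally, consent pages were removed from the reviewed text, and the patient instructions listed in Appendix III are not shown. What subjects are actually told is unknown, so release in practice is not demonstrated. A consistent consent form would still leave the protocol and the eligibility form in disagreement.

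**Conclusion.** The inconsistency is real. Criterion 11 and the Appendix III form differ from Section 9.2 in duration, anchor event, population and methods, and no text in the documents reconciles them. For subjects who can become pregnant, the end dates differ by between 0 and 8 months, depending on how and when participation ends. The size is conditional on the meaning of participation, which the undefined Long-Term Follow-up Study Period leaves open; the existence of the conflict does not depend on it.

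A reader might go further and infer that men and women should have the same coverage, or that one of the two periods is correct. The documents do not settle either question. Both are clinical decisions, and no view is taken here.

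**What to change.** Reconcile Section 5.1 criterion 11, Section 9.2 and item 11 of the Appendix III form so that all three state the same duration, anchor event, covered population and accepted methods. Define when study participation ends, including whether the Long-Term Follow-up Study Period in Section 10.3 counts and how long it lasts. The clinical team decides the content of each element.

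The cost is amendment wording and a matching form change. No endpoint, sample size, power or analysis is affected.
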